Appendix D: Recommended evaluation for MF/SS patients

Recommended evaluation/initial staging of the patient with MF/Sézary syndrome

Complete physical examination including

- Determination of type(s) of skin lesions
 - If only patch/plaque disease or erythroderma, then estimate percentage of body surface area involved and note any ulceration of lesions
 - If tumors are present, determine total number of lesions, aggregate volume, largest size lesion, and regions of the body involved
- Identification of any palpable lymph node, especially those >1.5 cm in largest diameter or firm, irregular, clustered, or fixed
- Identification of any organomegaly

Skin biopsy

- Most indurated area if only one biopsy
- Immunophenotyping to include at least the following markers: CD2, CD3, CD4, CD5, CD7, CD8, and a B-cell marker such as CD20. CD30 may also be indicated in cases where lymphomatoid papulosis, anaplastic lymphoma, or large-cell transformation is considered.
- Evaluation for clonality of TCR gene rearrangement

Blood tests

- CBC with manual differential, liver function tests, LDH, comprehensive chemistries
- TCR gene rearrangement and relatedness to any clone in skin
- Analysis for abnormal lymphocytes by either Sézary cell count with determination absolute number of Sézary cells and/or flow cytometry (including CD4+/CD7- or CD4+/CD26-)

Radiologic tests

- In patients with T1N0B0stage disease who are otherwise healthy and without complaints directed to a specific organ system, and in selected patients with T2N0B0disease
- with limited skin involvement, radiologic studies may be limited to a chest X-ray or ultrasound of the peripheral nodal groups to corroborate absence of adenopathy
- In all patients with other than presumed stage IA disease, or selected patients with limited T2 disease and the absence of adenopathy or blood involvement, CT scans of chest, abdomen, and pelvis alone±FDG-PET scan are recommended to further evaluate any potential lymphadenopathy, visceral involvement, or abnormal laboratory tests. In patients unable to safely undergo CT scans, MRI may be substituted.

Lymph node biopsy

- Excisional biopsy is indicated in those patients with a node that is either ≥ 1.5 cm in diameter and/or is firm, irregular, clustered, or fixed
- Site of biopsy
 - Preference is given to the largest lymph node draining an involved area of the skin or if FDG-PET scan data are available, the node with highest standardized uptake value (SUV).
 - If there is no additional imaging information and multiple nodes are enlarged and otherwise equal in size or consistency, the order of preference is cervical, axillary, and inguinal areas.
- Analysis: pathologic assessment by light microscopy, flow cytometry, and TCR gene rearrangement.

Appendix E: ISCL/EORTC staging of MF and SS patients

TNMB Stages	Description of TNMB
Skin[*]	
T ₁	Limited patches, papules, and/or plaques covering < 10% of the skin surface; may further stratify into T _{1a} (patch only) v T _{1b} (plaque ± patch)
T ₂	Patches, papules, or plaques covering ≥ 10% of the skin surface; may further stratify into T _{2a} (patch only) v T _{2b} (plaque ± patch)
T ₃	One or more tumors (≥ 1 cm diameter)
T ₄	Confluence of erythema covering ≥ 80% body surface area
Node[†]	
N ₀	No clinically abnormal lymph nodes; biopsy not required
N ₁	Clinically abnormal lymph nodes; histopathology Dutch grade 1 or NCI LN ₀₋₂
N _{1a}	Clone negative
N _{1b}	Clone positive
N ₂	Clinically abnormal lymph nodes; histopathology Dutch Grade 2 or NCI LN ₃
N _{2a}	Clone negative
N _{2b}	Clone positive
N ₃	Clinically abnormal lymph nodes; histopathology Dutch grade 3-4 or NCI LN ₄ ; clone positive or negative
N _x	Clinically abnormal lymph nodes without histologic confirmation or inability to fully characterize the histologic subcategories
Visceral	
M ₀	No visceral organ involvement
M ₁	Visceral involvement (must have pathology confirmation and organ involved should be specified)
Blood	
B ₀	Absence of significant blood involvement: ≤ 5% of peripheral blood lymphocytes are atypical (Sézary) cells
B _{0a}	Clone negative
B _{0b}	Clone positive
B ₁	Low blood tumor burden: > 5% of peripheral blood lymphocytes are atypical (Sézary) cells but does not meet the criteria of B ₂
B _{1a}	Clone negative
B _{1b}	Clone positive
B ₂	High blood tumor burden: ≥ 1,000/µL Sézary cells with positive clone [‡] ; one of the following can be substituted for Sézary cells: CD4/CD8 ≥ 10, CD4+CD7- cells ≥ 40% or CD4+CD26- cells ≥ 30%

- Abbreviations: ISCL, International Society for Cutaneous Lymphomas; EORTC, European Organisation for Research and Treatment of Cancer; MF, mycosis fungoides; SS, Sézary syndrome; NCI, National Cancer Institute.
- ~~§*~~ Patch = any size lesion without induration or significant elevation above the surrounding uninvolved skin: pokiloderma may be present. Plaque = any size lesion that is elevated or indurated: crusting or poikiloderma may be present. Tumor = any solid or nodular lesion ≥ 1 cm in diameter with evidence of deep infiltration in the skin and/or vertical growth.
- ~~§†~~ Lymph node classification has been modified from 2007 ISCL/EORTC consensus revisions¹ to include central nodes. Lymph nodes are qualified as abnormal if > 1.5 cm in diameter.
- ~~§‡~~ The clone in the blood should match that of the skin. The relevance of an isolated clone in the blood or a clone in the blood that does not match the clone in the skin remains to be determined.

Modified ISCL/EORTC Revisions to the Staging of MF/SS

Stage	T	N	M	B
IA	1	0	0	0,1
IB	2	0	0	0,1
IIA	1,2	1,2X	0	0,1
IIb	3	0-2X	0	0,1
IIIA	4	0-2X	0	0
IIIB	4	0-2X	0	1
IVA1	1-4	0-2X	0	2
IVA2	1-4	3	0	0-2
IVB	1-4	0-3X	1	0-2

X clinically abnormal lymph nodes without histologic confirmation or inability to fully characterize histologic subcategories.

Appendix F: Modified Severity Weighted Assessment Tool (mSWAT)

Body Region	% BSA in Body Region	Assessment of Involvement in Patient's Skin		
		Patch*	Plaque†	Tumor‡
Head	7			
Neck	2			
Anterior trunk	13			
Arms	8			
Forearms	6			
Hands	5			
Posterior trunk	13			
Buttocks	5			
Thighs	19			
Legs	14			
Feet	7			
Groin	1			
Subtotal of lesion BSA				
Weighting factor		×1	×2	×4
Subtotal lesion BSA × weighting factor				

- NOTE. mSWAT score equals summation of each column line.
- Abbreviations: BSA, body surface area; mSWAT, modified Severity Weighted Assessment Tool.
- \triangle^* Any size lesion without induration or significant elevation above the surrounding uninvolved skin; poikiloderma may be present.
- $\triangle^†$ Any size lesion that is elevated or indurated; crusting, ulceration, or poikiloderma may be present.
- $\triangle^‡$ Any solid or nodular lesion ≥ 1 cm in diameter with evidence of deep infiltration in the skin and/or vertical growth.

Appendix G : Ann Arbor Staging System

Stage I

Either of the following means the disease is stage I:

- The lymphoma is in only 1 lymph node area or lymphoid organ such as the thymus (I).
- The cancer is found only in 1 area of a single organ outside of the lymph system (IE).

Stage II

Either of the following means the disease is stage II:

- The lymphoma is in 2 or more groups of lymph nodes on the same side of (above or below) the diaphragm (the thin band of muscle that separates the chest and abdomen). For example, this might include nodes in the underarm and neck area but not the combination of underarm and groin nodes (II).
- The lymphoma extends from a single group of lymph node(s) into a nearby organ (IIE). It may also affect other groups of lymph nodes on the same side of the diaphragm.

Stage III

Either of the following means the disease is stage III:

- The lymphoma is found in lymph node areas on both sides of (above and below) the diaphragm.
- The cancer may also have spread into an area or organ next to the lymph nodes (IIIE), into the spleen (IIIS), or both (IIISE).

Stage IV

Either of the following means the disease is stage IV:

- The lymphoma has spread outside of the lymph system into an organ that is not right next to an involved node.
- The lymphoma has spread to the bone marrow, liver, brain or spinal cord, or the pleura (thin lining of the lungs).

Other modifiers may also be used to describe the lymphoma stage:

Appendix H: Romidepsin Prescribing Information

**Revision History:**

VERSION	CHANGE DESCRIPTION	AUTHOR	DATE
FINAL 1.0	Not Applicable	[REDACTED]	09AUG2021

## List of Abbreviations

Abbreviation	Term
AE	Adverse Event
ATC	Anatomical Therapeutic Chemical
BID	Twice Daily
CI	Confidence Interval
CR	Complete Response
CT	Computed Tomography
CTCAE	Common Terminology Criteria for Adverse Events
CTCL	Cutaneous T cell lymphoma
DCR	Disease Control Rate
DLT	Dose Limiting Toxicity
DoR	Duration of Response
DRC	Data Review Committee
ECG	Electrocardiogram
ECOG PS	Eastern Cooperative Oncology Group Performance Status
eCRF	Electronic Case Report Form
FAS	Full Analysis Set
FDA	Food and Drug Administration
HDAC	histone deacetylases
IEC/IRB	Independent Ethics Committee/ Institutional Review Board
IV	Intravenous
MedDRA	Medical Dictionary for Regulatory Activities
mITT	Modified Intent-to-Treat
mSWAT	Modified Severity-Weighted Assessment Tool
MTD	Maximum Tolerated Dose
NCI	National Cancer Institute
ND	Not Done
NE	Not Evaluable
ORR	Objective Response Rate
P13K	phosphoinositide-3-kinase
PK	Pharmacokinetics
PP	Per-Protocol
PR	Partial Response
PT	Preferred Term
PTCL	Peripheral T-cell lymphoma
Q1	First Quartile
Q3	Third Quartile
QTcF	QT interval with Fridericia's correction
SAE	Serious Adverse Events
SAP	Statistical Analysis Plan
SAS	Statistical Analysis Software
SD	Stable Disease
SOC	System Organ Class
SRC	Scientific Review Committee
TCL	T-cell lymphoma
TEAE	Treatment-Emergent Adverse Event
WHO	World Health Organization

## 1. Amendments from Previous Version(s)

Not Applicable.

## 2. Introduction

Note: In this document, any text taken directly from the protocol (Number: RP6530+Romidepsin -1805, Amendment 1 to Version 1.0 Dated 16 August 2018, Amendment version dated 30 November 2018) is *italicized*.

This SAP provides the detailed methodology for summary and statistical analyses of the data collected in study RP6530+Romidepsin-1805. This document may modify the plans outlined in the final protocol.

### 2.1 Rationale

*Tenalisib is a highly specific and orally available dual kinase PI3K (phosphoinositide-3-kinase) δ/γ inhibitor with nano-molar inhibitory potency and several fold selectivity over α and β PI3K isoforms. The specificity of Tenalisib towards PI3K δ and γ is evidenced by >1000 and >100-fold selectivity over α and β isoforms in an enzyme-based assay. Chemically, Tenalisib is an iso-flavone substituted adenine.*

*Romidepsin is a histone deacetylases (HDAC) inhibitor and was approved by FDA for the treatment of CTCL and PTCL in 2009 and 2011 respectively for the patients who have received at least one prior systemic therapy.*

*Given the fact that both Romidepsin and Tenalisib have non-overlapping toxicity profiles, half of the optimal dose of Tenalisib (400 mg BID) and one dose below the approved dose of Romidepsin (12 mg/m2) are considered reasonable as starting doses of the combination from safety point of view. It is expected that proposed combination of Tenalisib with Romidepsin has the potential to improve response rates and increase the durability of response.*

## 3. Study Objectives

### 3.1 Primary Objective

- *To characterize safety, tolerability and to establish the maximum tolerated dose (MTD) of Tenalisib in combination with Romidepsin in patients with R/R T-cell lymphoma.*

### 3.2 Secondary Objectives

- *To assess the preliminary anti-tumor activity of various dose levels of Tenalisib in combination with Romidepsin as determined by the Objective Response Rate (ORR) and Duration of Response (DoR).*

- *To characterize the Pharmacokinetics (PK) of Tenalisib and Romidepsin when given in combination.*

### 3.3 Exploratory Objective

- *To correlate clinical efficacy with markers that include but are not limited to quantitative and qualitative measurements of malignant cells, cytokines, and chemokines in blood/serum.*

## 4. Study Endpoints

### 4.1 Primary Endpoint

- **Safety**
  - *Adverse Event (AE), Grade 3/ 4 AEs, Serious and fatal Adverse Event (SAE), graded using NCI CTCAE Version 5.0.*

### 4.2 Secondary Endpoints

- **Efficacy**
  - *Objective Response Rate (ORR), defined as sum of CR and PR rates, assessed according to the Lugano Classification for initial evaluation, staging, and response assessment of Hodgkin/non-Hodgkin lymphoma in PTCL patients; and according to the modified Severity Weighted Assessment Tool (mSWAT) in CTCL patients.*
  - *Duration of Response (DoR), calculated as time from the initial response to documented disease progression.*
- **Pharmacokinetics**
  - *PK Parameters [AUC(0-∞), AUC(0-t), Cmax, tmax, Kel, and t1/2] of Tenalisib and Romidepsin.*

### 4.3 Correlative/ Exploratory Endpoints

- *Correlative markers include baseline and on-treatment serum levels of chemokines, cytokines, antibodies to tumor antigens, and other immune mediators (e.g. sIL2R and CTACK for PTCL; CD30, IL-31 and IL-32 for CTCL) as deemed relevant by the sponsor.*

## 5. Study Design

*This is a multi-center, open label, non-randomized, two-part Phase I/II study of Tenalisib in combination with Romidepsin in adult patients with relapsed/refractory TCL. The first part is an open-label, 3+3 dose escalation, Phase I study for MTD determination. The second part is a Phase II, dose expansion to delineate the safety and anti-tumor activity of the combination at the MTD/optimal dose.*

*In dose escalation, a minimum of 2 and maximum 18 patients will be enrolled in three dose levels unless additional dose levels are required to reach MTD/ optimal dose. In dose expansion,*

up to 24 TCL patients will be enrolled (Group 1= 12 PTCL patients and Group 2= 12 CTCL patients).

The study will end when all ongoing subjects have reached their third tumor assessment on Cycle 8/Day 1 (C8D1) or have discontinued from the study for any reason, whichever is earlier. At the end of the study, all ongoing patients with no evident disease progression will be given the opportunity to enroll in an open-label compassionate use study protocol and will be followed up.

## 5.1 Phase I: Dose escalation

Sequential dose escalation will begin with Cohort 1. A minimum of three patients will be enrolled at each dose level. Dose levels will be increased in successive increments according to the dose escalation cohorts mentioned in the table below. Escalation to the next cohort will occur if no patient within a three-patient cohort or one in six patients experiences a dose limiting toxicity (DLT). De-escalation to different lower doses in case DLT criteria is met, will be done as per the discretion of Safety Review Committee (SRC). The highest doses of the combination (Tenalisib at 800 mg BID plus Romidepsin IV 14 mg/m^2) will be considered as optimal in case there is no DLT at this dose level.

### Dose escalation scheme:

Cohort	N	Tenalisib 	Romidepsin 
Cohort 1	3-6	Tab. 400 mg PO twice a day	IV 12 mg/m  on Day 1, 8 and 15
Cohort 2	3-6	Tab. 600 mg PO twice a day	IV 12 mg/m  on Day 1, 8 and 15
Cohort 3	3-6	Tab. 800 mg PO twice a day	IV 14 mg/m  on Day 1, 8 and 15

Note: Alternate dose levels/dosing schedules may be considered by the SRC if deemed essential based on emerging safety and PK data.

In case the dose (e.g. 800 mg BID) is leading to DLT of the combination, the dose of Tenalisib will be reduced to lower dose (e.g. 600 mg BID) and will be evaluated for safety in a separate cohort.

In case the dose (e.g. 14 mg/m^2) is leading to DLT of the combination, the dose of Romidepsin will be reduced to lower dose (e.g. 12 mg/m^2) and if required further to 10 mg/m^2 and will be evaluated for safety in a separate cohort.

**DLT assessment:** The data of at least 3 patients will be required for DLT assessment. DLT assessment period will be 28-days (inclusive) (will begin on C1D1 and end on C2D1), unless extended by the medical monitor. In the first cycle, patients must have been treated with at least 2 doses of Romidepsin and minimum 14 days with Tenalisib to be considered eligible for safety analysis unless identified to have a DLT. Patients who experience a DLT will be considered evaluable regardless of the number of doses received.

Individual patients will be considered for **Intra-subject dose escalation** at the discretion of investigator after discussion with medical monitor.

## 5.2 Phase II: Dose Expansion

After establishing the MTD/optimal dose, the Phase II (expansion part) will be opened as approved by the SRC to enroll two groups of patients.

Group	N	Patient Population	Tenalisib	Romidepsin
-------	---	--------------------	-----------	------------

Group 1	12	Patients with R/R PTCL	MTD/ Optimal dose	MTD/ Optimal dose on Day 1, 8 and 15
Group 2	12	Patients with R/R CTCL	MTD/ Optimal dose	MTD/ Optimal dose on Day 1, 8 and 15

### 5.2.1 Number of subjects

- *Phase I: Total 2-18 patients will be enrolled in 3 escalating cohorts unless additional dose levels are required to reach MTD/ optimal dose.*
- *Phase II: Total 24 patients with relapsed/refractory TCL will be enrolled.*

### 5.3 Study Stopping Rules

- ***Stopping Rule for Dose Escalation:*** *The SRC will be in charge of reviewing safety data following the final treatment dose (Day 28 of Cycle 1) of the last patient in each cohort and will decide whether or not it is possible to proceed to the next cohort.*
- ***Suspension of Patient Enrollment:*** *In the event of one (1) death attributed to the study drug, study accrual will be suspended pending further investigation, and will only be resumed at the recommendation of the SRC. The SRC will have discretion to terminate the trial if an additional death occurs that can be attributed to the study drug.*
- ***Stopping Rule for Dose Expansion:*** *After establishing the MTD/optimal dose, the Phase II expansion part will be opened as approved by the SRC. The SRC will continue to monitor safety of the combination (or toxicity trends that may be of concern) at interval of 3 months from initiation of expansion cohort till the completion of the study. Safety/toxicity will be monitored across cohorts combined together. The SRC will have discretion to terminate the trial if there are major safety concerns.*
- ***Study Stopping:*** *Sponsor reserves the right to terminate the study in the interest of patient safety, for noncompliance with the protocol, lack of recruitment or any other administrative reasons. The sponsor and PIs will notify the regulatory authority and respective IRB/IEC respectively if the trial terminates early, with a justification for the early termination.*

## 6. Sample Size Considerations

***Part 1: In Dose Escalation, three patients per cohort are considered appropriate for the assessment of overall safety and tolerability and for providing adequate confidence for dose escalation. No formal sample size and power analysis is done. Accordingly, total 2-18 patients will be enrolled in 3 escalating cohorts unless additional dose levels are required to reach MTD/ optimal dose. Optimal dose will be determined by the SRC.***

***Part 2: Total 24 patients with relapsed/refractory TCL will be enrolled in two groups (12 patients in each group). Twelve patients per group is considered appropriate for assessment of preliminary anti-tumor activity of the combination. However, the SRC may modify the sample size due to unforeseen clinical situations.***

## 7. Analysis Populations

### 7.1 All Enrolled Patients

The enrolled patients are those who have consented and screened with eligibility verified as per the Inclusion-Exclusion criteria mentioned in study protocol.

### 7.2 Safety Population Set

*The Safety Population set will include all subjects who receive at least 1 dose of the study medication.* This set will be used for reporting safety data, patient demographic data and any available patient baseline characteristics as reported in the Case Report Form (CRF).

### 7.3 Modified Intent-to-Treat Population (mITT) Analysis Set

*The mITT is the primary efficacy analysis population and will include data from all patients who received at least 1 dose of study medication and provide at least 1 post-baseline efficacy assessment.*

Note: In order to offer sufficient time for assessing the effectiveness of the study medications, patients who provide the post-baseline efficacy assessment; at least on Cycle 3 Day 1 or are discontinued from study at Cycle 3 Day 1 shall be evaluated for mITT analysis set.

Programmatically, if the patient received at least 1 dose of study medication and have provided at least Cycle 2 Day 22 efficacy assessment, then he/she will be qualified for mITT analysis set.

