14. **A bone marrow biopsy:** PTCL: Bone marrow biopsy should be collected ≤ 12 weeks prior to C1D1 and/or to confirm a complete response to the study drug. If patient has negative bone marrow at baseline, there is no need to have it repeated to confirm CR. Additional biopsy will be obtained if clinically indicated. The CTCL patients with predominantly blood involvement (B₂) will have a bone marrow biopsy at screening (unless it has been shown to be negative within the last 6 months) and as indicated to confirm a complete response.
15. **Skin biopsy:** In CTCL patients, skin biopsy should be performed at screening, and to confirm a complete response. Historical data of 12 weeks is acceptable.
16. **Radiological scan:** In PTCL and CTCL patients with nodal and visceral involvement, PET and “diagnostic quality” CT scan will be performed at the time of screening within 28 days of screening. Following screening, CT scans should be repeated at C3D1 (± 7 days), C5D1 (± 7 days) and C8D1 (± 7 days). PET should be done at C3D1 (± 7 days) and to confirm CR. Tumor imaging should remain consistent throughout study and should include those thought by investigator to best capture status of disease. Baseline scans, if already available as SOC within 28-days of screening is accepted as part of study protocol.
17. **Skin assessment:** In all CTCL patients, mSWAT will be performed at the time of screening within 28 days of screening and at C3D1 (± 7 days), C5D1 (± 7 days) and C8D1 (± 7 days). Disease response assessment will be performed at C3D1 (± 7 days), C5D1 (± 7 days) and C8D1 (± 7 days) and/ or at the EOT or as clinically indicated using mSWAT.
18. **Skin photograph:** In CTCL patients, skin lesion photograph will be taken at screening, at the time of response (PR/CR/PD) and at other time points as required by the PI.
19. Tenalisib will be administered orally twice a day in 28-days of cycle for 7 Cycles in absence of disease progression or toxicity warranting discontinuation of therapy. On the day of Romidepsin administration, the morning dose of Tenalisib should be given in clinic one hour prior to Romidepsin infusion. Patient will receive Tenalisib at the start of each cycle (C1D1, C2D1, C3D1 ...).
20. Romidepsin will be administered as an intravenous infusion over 4 hours unless progression of disease or toxicity warranting discontinuation of therapy.

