9.3 Study Population

The following 3 analysis populations are planned for this study:

- Modified Intent-to-Treat Population (mITT): the mITT is the primary efficacy analysis population and will include data from all patients who received at least 1 dose of study medication and provide at least 1 post-baseline efficacy assessment.
- Per-Protocol (PP) Population: the PP Population is a subset of the modified Intent-to-Treat Population and will include patients without major protocol deviations.
- Safety Population: The Safety Population will include all subjects who receive at least 1 dose of the study drug.

Membership in the analysis populations will be determined before database lock.

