### 10.5.3 Best Overall Response (BOR)

It is the best response, as assessed and confirmed by site PI, from the start of the treatment until disease progression or discontinuation from the study.

This data will be summarized using frequency and percentage for CR, PR, SD, and PD, as reported in the CRFs for overall subjects. This data will also be listed.

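### SAP 7.3 adds a Day 50 floor to mITT that protocol 9.3 lacks, so a patient with documented early progression can leave the ORR denominator

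*SAP*

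**What the plan says.** **Protocol.** Section 9.3 defines mITT, the primary efficacy population, as patients who had at least one dose and "provide at least 1 post-baseline efficacy assessment". It sets no minimum time. Section 8.1 defines evaluability for response by a baseline evaluation plus any one later evaluation, again with no time limit.

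**SAP 7.3** makes three statements:

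1. The first sentence repeats the protocol definition.
2. A Note adds timing. Its reason is "In order to offer sufficient time for assessing the effectiveness of the study medications". It asks for an assessment at C3D1 at least, and offers a second route for patients who "or are discontinued from study at Cycle 3 Day 1 shall be evaluated for mITT analysis set".
3. A programming sentence says that if a patient had at least one dose and "have provided at least Cycle 2 Day 22 efficacy assessment, then he/she will be qualified for mITT analysis set". It does not mention the discontinuation route.

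**Use of the sets.** SAP 10.5 runs efficacy on mITT and PP only, and SAP 7.4 makes PP a subset of mITT. SAP 10.5.3 takes best overall response "from the start of the treatment until disease progression or discontinuation from the study" and reports "frequency and percentage for CR, PR, SD, and PD".

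**Authority to change.** SAP 2 states: "This document may modify the plans outlined in the final protocol".

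**The concern.** The Note and the programming sentence are one timing rule, because Day 50 is the lower edge of the C3D1 window. That leaves two gaps. The floor conflicts with the definition in the first sentence of the same section, and the programming sentence drops the Note's discontinuation route, which is itself unclear about patients who stop before C3D1.

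The patient most exposed is one who progresses early, has this documented, and is not assessed again. Under protocol 9.3 that patient is a non-responder in the denominator. Under the programmed rule the patient is absent from ORR, DCR and the PD row of the best-response table. Waiting for an effect may be a fair reason to set aside an early stable disease reading. It is no reason to set aside progression, which is already an outcome.

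No efficacy rate would recover the patient. PP inherits the exclusion, and the swimmer plot in SAP 10.6.1, though on the Safety set, shows only the C3D1 response. Disposition counts and listings would let a reader trace who was excluded, but no ORR or DCR table would count them.

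**Working it through.** **1. Day of the floor.** With 28-day cycles, study day = 28 × (cycle − 1) + day.

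- C2D22: 28 + 22 = Day 50
- C3D1: 56 + 1 = Day 57

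Both match Protocol Table 5. The C3D1 response window of ±7 days is Days 50–64, so the floor is the opening of the first scheduled response window.

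**2. Can a patient's only assessment fall before Day 50?** Yes, by the protocol's own procedures.

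- Section 8.2 also calls for response assessment at EOT, or when clinical progression is suspected.
- PTCL: section 6.12 places EOT within 7 days of the last dose or discontinuation and waives the scan only if one was done within 28 days. The latest baseline scan is Day 0, so an EOT on Day 29 is 29 days later and a scan is due, unless an earlier post-baseline scan exists. Section 8.2 stops treatment at progression and requires imaging only until progression is documented.
- CTCL: Table 6 footnote 17 also places response assessment "at the EOT or as clinically indicated using mSWAT". The 28-day waiver names only radiology and bone marrow, and Tables 5 and 6 schedule no disease assessment after EOT.

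Progression documented on Day 35, for example, satisfies protocol 9.3 and fails the programmed rule.

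**3. Effect on the rates.** Responder and stable disease counts are assumed; intervals are exact binomial 95%. ORR = responders / (n − removed).

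| Case | ORR | 95% CI |
|---|---|---|
| Group of 12, none removed | 3/12 = 25.0% | 5.5–57.2 |
| One progressor removed | 3/11 = 27.3% | 6.0–61.0 |
| Two progressors removed | 3/10 = 30.0% | 6.7–65.2 |
| Both groups, none removed | 6/24 = 25.0% | 9.8–46.7 |
| Both groups, one progressor removed | 6/23 = 26.1% | 10.2–48.4 |

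**4. Direction by type of patient removed.** Assume 3 responders and 3 SD of 12.

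| Removed | ORR | DCR |
|---|---|---|
| None | 3/12 = 25.0% | 6/12 = 50.0% |
| One progressor | 3/11 = 27.3% | 6/11 = 54.5% |
| One early SD | 3/11 = 27.3% | 5/11 = 45.5% |
| One early PR | 2/11 = 18.2% | 5/11 = 45.5% |

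Removing a progressor always raises both rates (while each is above zero). The net effect on DCR depends on the mix.

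**5. How many in PTCL?** The documents give no count. Protocol 1.2 cites a romidepsin PFS of 4 months in PTCL. Treat this as an exponential median, with 30.44 days per month (4 months = 121.75 days) and Day 1 as time 0. The share with an event after Day 29 and up to Day 49 is

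exp(−ln 2 × 28/121.75) − exp(−ln 2 × 48/121.75) = 9.2%, and 12 × 9.2% ≈ 1.1 patients.

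At an assumed 8 months it is 5.1%, or about 0.6 of 12. For that window this is an upper end, since it includes deaths without assessment and progression first seen at the Day 50–64 scan. It does not bound all progression before Day 50, because unscheduled assessments can fall before Day 29. No CTCL PFS is given, so no CTCL number is estimated.

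**The case against.** Four points have weight.

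- **Wording.** The programming sentence is conditional and does not say *only if*. The protocol definition stands unrevoked at the head of SAP 7.3, and the discontinuation route could be a loose attempt to keep patients who stopped by C3D1. This stands as to certainty: exclusion is the natural reading, not an explicit one. But the Note's purpose makes sense only if earlier assessments do not qualify. If nobody is to be excluded, the sentence has no function.
- **Permission.** SAP 2 and protocol section 9 both allow the analysis plan to change. A time-based evaluability rule also has a precedent in protocol 1.1.2, where the earlier study reported ORR in 35 evaluable patients with at least two cycles. So departing from the protocol is not in itself an error. That permits the change but gives no reason to drop documented progression.
- **Size.** One patient moves ORR by 2.3 points (27.3 − 25.0) against intervals more than 50 points wide, in a secondary endpoint with no hypothesis test (SAP 9.1). The estimate of 1.1 of 12 covers one sub-window and rests on a single-agent figure that the protocol does not call a median. This stands and limits the severity.
- **Remedy.** Neither document calls for a second table on all treated patients. Agreed: it is optional, and the correction does not depend on it.

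**Conclusion.** The concern holds. On its natural reading, the programmed mITT excludes a patient with progression documented before Day 50 and no later assessment, whom protocol 9.3 keeps as a non-responder. The resulting bias in ORR is upward for every such patient. The conflict in the text is certain; the number affected is not known, and the illustrations rest on assumed counts.

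This should be fixed, but it does not threaten the trial: ORR is secondary and descriptive, and the primary safety and MTD objective is unaffected.

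**What to change.** - **SAP 7.3:** delete the Cycle 2 Day 22 sentence, and delete the Note or reconcile it with protocol 9.3, so that any post-baseline assessment qualifies a dosed patient and any progression documented before C3D1 counts as non-response.
- **SAP 10.5.1, optional:** show ORR and DCR on the Safety Population beside mITT, with both denominators. Count unassessed patients as non-responders, and exempt this block from the SAP 10 rule that bases percentages on non-missing assessments.

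The cost is SAP wording before database lock, when SAP 7.4 says population membership is settled. The supplement is one extra table block with no new data. The reported ORR may be slightly lower.
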